10.8.2 ECG Evaluations

All ECG data will be listed by treatment, subject and visit/time, abnormalities will be flagged. Summary statistics will be provided by treatment and visit/time.

10.8.3 Clinical Laboratory Evaluations

All laboratory data will be listed by treatment, subject, and visit/time and abnormalities will be flagged. Summary statistics will be provided by treatment and visit/time.

10.8.4 Adverse Events

All information obtained on adverse events will be displayed by treatment and subject.

The number and percentage of subjects with adverse events overall, treatment emergent AEs (TEAEs), related TEAEs, TEAEs leading to discontinuation of study drug or study and serious TEAEs will be tabulated by System Organ Class and preferred term with a breakdown by treatment. A subject with multiple adverse events within a body system is only counted once towards the total of this body system.

10.8.5 Pharmacokinetics

Population PK will be performed on all subjects. The PK analysis of MAU868 plasma concentration data will be performed using validated software in order to derive the population mean (and variance) values of specific PK parameters. Plasma concentrations will be summarized descriptively by time point of collection.

The PK endpoints for MAU868 are: area under the concentration-time curve to the end of the dosing period (AUC_{0-24}), area under the concentration-time curve up to the last measurable concentration ($AUC_{0-\text{last}}$), concentration at the end of infusion (C_{eoI}) and minimum concentration observed (C_{trough}). Plasma samples for pharmacokinetic (PK) evaluations will be collected at the time points described in the Schedule of Events ([Appendix A](#)).

Results of the PK analysis will be reported separately.

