3.2.2 Exclusion Criteria

Subjects who meet any of the following criteria will not be eligible for entry into the study:

- 1. A BK plasma viral load which has exceeded 10^3 copies/mL for >4 months.
- 2. A BK plasma viral load of $\geq 10^7$ copies/mL.
- 3. Are receiving, at the time of informed consent, mTOR inhibitors.
- 4. Kidney transplant recipients who are anticipated to require Intravenous Immune Globulin (IVIG) treatment during the study period or who have received IVIG in the previous 9 months.
- 5. Kidney transplant recipients who, in the opinion of the Investigator, are likely to require antibody-depletion. Antibody-depleting therapies include but are not necessarily limited to hemodialysis, plasmapheresis and immunoadsorption.
- 6. Treatment within the previous month with the following medications: cidofovir, leflunomide.
- 7. History of hypersensitivity or intolerance to intravenous or subcutaneous administration of biologic medications or to any of the excipients included in the formulation of MAU868.
- 8. Platelet count $<50,000/\text{mm}^3$ at the time of informed consent, as determined by local laboratory.
- 9. History of splenectomy or asplenia.
- 10. Are lactating and/or pregnant.
- 11. Use of other investigational drugs at the time of enrollment, or within 5 half-lives of enrollment, or until the expected PD effect has returned to baseline, whichever is longer; or longer than 5 half-lives if required by local regulations.
- 12. Prior exposure to MAU868.

13. Any other condition or laboratory abnormality that, in the opinion of the Investigator or the Sponsor, would put the patient at unacceptable risk for participation in the study or would interfere with the assessments included in the study.

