5.3 Study Drug Administration

Study drug should be administered only at clinical sites. All clinical sites must have the appropriate equipment and trained personnel needed to effectively manage hypersensitivity reactions including anaphylaxis and infusion reactions.

Cohort 1 MAU868 Arm:

- MAU868 1350 mg IV over at least 60 minutes approximately every 28 days for a total of 4 doses.

Cohort 2 MAU868 Arm:

- MAU868 6750 mg IV over at least 180 minutes on Study Day 1, then 1350 mg IV over at least 60 minutes for subsequent doses approximately every 28 days for a total of 4 doses.

Cohort 3 MAU868 Arm:

- MAU868 6750 mg IV over at least 180 minutes approximately every 28 days for a total of 4 doses.

Placebo

- Cohort 1: Placebo (D5W) will be administered as an IV infusion over at least 60 minutes approximately every 28 days for a total of 4 doses.
- Cohort 2: Placebo (D5W) will be administered as an IV infusion over at least 180 minutes on Day 1 and then over 60 minutes approximately every 28 days for a total of 4 infusions.
- Cohort 3: Placebo (D5W) will be administered as an IV infusion over at least 180 minutes approximately every 28 days for a total of 4 infusions.
- Placebo is prepared as a standard 250 mL volume of intravenous fluid.

All infusions will be followed by at least a 25 mL D5W flush to run at the same infusion rate as the dose of study drug.

Refer to the Pharmacy Manual for additional dose preparation and administration instructions.

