MAU868 levels in serum will be determined by a validated ELISA-based method. A detailed description of the method used will be included in the PK bioanalytical data report. The anticipated LLOQ is 50.0 ng/mL. Concentrations will be expressed in mass per volume units (e.g., ng/mL). Missing values or those concentrations below the LLOQ will be labeled as such in the data listings and reported as "zero" in data presentations and calculations.

MAU868 serum concentration data will be listed by subject and visit/sampling time point. Descriptive summary statistics of trough levels will be provided by visit/sampling time point, including the frequency (n, %) of concentrations below the LLOQ and reported as zero. Summary statistics will include mean (arithmetic and geometric), SD, CV (arithmetic and geometric), median, minimum and maximum. Concentrations below LLOQ will be treated as zero in summary statistics.

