10.8.6 Interim Analysis

Interim Analyses

Following completion of the 12-week treatment period of Cohort 1, unblinded safety and tolerability data (adverse events, clinical laboratories, vitals/physical exams and ECGs), efficacy data (BKV viral load in the plasma) and PK (MAU868 plasma levels) will be reviewed by the Sponsor Study Review Committee (SSRC). The treatment assignment in Cohort 1 will be unblinded; however, these data will not include associated subject or site identifiers. The objectives of this interim analysis are to evaluate whether four doses MAU868 1350 mg IV administered every 28 days for a total of 4 doses demonstrate:

- safety and tolerability signals compared to placebo
- a decrease in BK plasma viral load compared to placebo
- predicted MAU868 plasma levels

The conclusions from this first analysis will be used by the Sponsor to evaluate the safety and efficacy of MAU868 early-on in this first-in-patient study. Unless a significant safety issue related to administration of MAU868 has been identified, the conclusions will have no impact on Cohort 2 or the study's design.

Following completion of the 12-week treatment periods for Cohorts 1 and 2, cumulative unblinded data from both cohorts will be reviewed for safety and tolerability (adverse events, clinical laboratories, vitals/physical exams and ECGs), efficacy (BKV viral load in the plasma) and PK (MAU868 plasma levels). The treatment assignments will be unblinded; however, these data will not include associated subject or site identifiers. The objectives of this second interim analysis are to evaluate whether four doses MAU868 1350 mg IV administered every 28 days for a total of 4 doses or MAU868 6750 mg IV administered as a first dose followed by 3 more doses of MAU868 1350 mg IV administered every 28 days demonstrate:

- safety and tolerability signals compared to placebo
- a decrease in viral load compared to placebo
- predicted MAU868 plasma levels

Based on the SSRC's safety, efficacy and PK conclusions for Cohorts 1 and 2, the dosing regimen for Cohort 3 may be *adjusted* in dosage and/or duration; however, the dosage and duration for Cohort 3 will not exceed the dose already specified in the protocol. Cohort 3 will not be opened for screening and enrollment this evaluation has been completed

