13. Three PK samples should be collected on Study Day 1 (first dose administration) and Study Day 84 (last dose administration) : within approximately 30 minutes prior to the start of the infusion, within approximately 30 minutes following the end of the infusion and between approximately 3-6 hours after the end of infusion.
14. On Study days 28 and 56 (2nd and 3rd dose administrations), two PK samples should be collected: within 30 minutes prior to the start of infusion and within 30 minutes following the end of infusion.
15. Any anti-donor antibodies collected by the site should be recorded in the eCRF, but collection is not mandatory.
16. Only for females of child-bearing potential. A negative urine or serum pregnancy test performed locally within 96 hours prior to Study Day 1 (Baseline). Local urine dipstick or serum pregnancy testing should be performed before infusions #2 on Day 28, #3 on Day 56 and #4 on Day 84.
17. Vital signs (temperature, blood pressure, heart rate, respiratory rate and oxygen saturation) should be obtained at each visit if the visit is in person. If the visit is not in person vital signs are not required. On drug infusion days, vitals should be taken within 30 minutes before starting the infusion, and then approximately every 30 minutes (+/- 10 minutes) after the start of the infusion until at least 2 hours after completing the infusion.
18. ECGs should be performed prior to dose administration on Study Day 1 and after dose administration on Study Day 84 and on Day 252 (or at the Early Termination Visit)
19. Blood and urine for safety should be collected and sent to the central laboratory. Laboratory tests used in for the management and monitoring of the subject per standard practice may be performed at the local laboratory at the Investigator's discretion.

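### Protocol 10.8.5 defines Ctrough and the dosing-period AUC in terms that conflict with the 28-day dosing interval and with the protocol's own use of trough, and the SAP does not correct them.

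*Protocol*

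**What the plan says.** Protocol 10.8.5 names four PK endpoints. Two matter here: the "area under the concentration-time curve to the end of the dosing period (AUC_{0-24", with no time unit, and the "minimum concentration observed (C_{trough", with no dosing interval, visit or post-dose restriction.

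The surrounding design is as follows.

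- **Dosing.** Protocol 5.3 gives, for Cohort 1, "MAU868 1350 mg IV over at least 60 minutes approximately every 28 days for a total of 4 doses". The other cohorts use the same spacing, with infusions on Days 1, 28, 56 and 84.
- **Sampling.** On Day 1 a PK sample is due "within approximately 30 minutes prior to the start of the infusion" (Appendix A, footnote 13; Appendix C). The last sample is on Day 252, 24 weeks after the fourth dose.
- **Day 1 status.** "Prior exposure to MAU868" is an exclusion criterion (3.2.2), so subjects have had no drug when the first sample is drawn.
- **Low values.** In the PK text of 10.5.1: "Concentrations below LLOQ will be treated as zero in summary statistics". The same text also reports missing values as zero.
- **Other uses of trough.** Protocol 1.4.2 equates trough with the concentration 28 days after a dose. Protocol 1.6 uses Ctrough at the end of treatment. The PK text of 10.5.1 summarises troughs visit by visit.
- **SAP.** Section 6.1.4 names serum concentrations and parameters estimated from them. Section 7.6 describes a compartmental model and refers to a standalone PK plan. Section 9 lists no PK change.

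**The concern.** A minimum over all observed samples is not a trough when the schedule includes a drug-free sample at one end and a washout sample at the other. An AUC that runs to the end of the dosing period cannot carry the subscript 0-24 when doses are 28 days apart. Whoever derives the parameters must either follow the words and obtain something the protocol does not otherwise mean by trough, or guess the intent.

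Pharmacokinetics is a secondary objective. The protocol's own predictions are an end-of-treatment trough, which supports the efficacy rationale, and a monthly AUC, which supports the safety margins. Parameters derived literally from 10.8.5 could not be set beside either prediction.

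**Working it through.** **1. The plan's AUC figures reproduce and are monthly.** From Protocol 1.6:

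- 1,420,000 / 206,231 = 6.89 (stated 6.9)
- 1,031,155 / 206,231 = 5.00 (stated 5.0)
- 1,420,000 / 1,031,155 = 1.38 (stated 1.4)

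The human values are steady-state exposures in µg·hr/mL for once-monthly dosing, so the AUC of interest covers a dosing interval.

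**2. What 24 could mean.**

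| Reading | Compared with the design |
|---|---|
| 24 hours | One day of a 28-day interval: 24 / (28 × 24) = 24 / 672 = 3.6% |
| 24 days | Not the 28-day interval |
| 24 weeks | The length of follow-up, not the 12-week treatment period |

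No reading agrees with the words beside the label.

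To illustrate the hours reading, take a one-compartment model. Clearance is dose / steady-state AUC = 1,350,000 µg / 206,231 µg·hr/mL = 6.55 mL/h. The documents give no volume, so I assume 3 to 7 L. With k = CL / V, the first-dose AUC over 24 h is (dose / CL) × (1 − exp(−24k)):

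- V = 3 L: 206,231 × 0.0510 = about 10,500 µg·hr/mL
- V = 7 L: 206,231 × 0.0222 = about 4,600 µg·hr/mL

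That is about 2% to 5% of the monthly figure.

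**3. The trough the protocol predicts.** Protocol 1.6 gives kidney exposure at Ctrough as a multiple of EC50, using a kidney coefficient of 13.7%. Reading the stated fold as a ratio, serum trough = fold × EC50 / 0.137.

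| Cohort | Genotype III (EC50 0.093 µg/mL) | Genotype I (EC50 0.009 µg/mL) |
|---|---|---|
| 1 | 253 × 0.093 / 0.137 = 171.7 | 2618 × 0.009 / 0.137 = 172.0 |
| 2 | 365 × 0.093 / 0.137 = 247.8 | 3775 × 0.009 / 0.137 = 248.0 |
| 3 | 1264 × 0.093 / 0.137 = 858.0 | 13,061 × 0.009 / 0.137 = 858.0 |

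Both ends of each range give the same serum value, so the back-calculation is consistent: about 172, 248 and 858 µg/mL.

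**4. The literal minimum.** The Day 1 pre-infusion sample is expected below the anticipated LLOQ of 50 ng/mL (0.05 µg/mL) and is therefore zero. With the step 2 model, four Cohort 1 doses and V of 3 to 7 L, the Day 252 concentration is about 0.09 to 8.8 µg/mL, still above LLOQ. In a fully sampled MAU868 subject the minimum over all samples is then the Day 1 zero. Leaving out Day 1 alone does not repair the wording, because the minimum could then be a washout value or a missing sample reported as zero.

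**5. Does the SAP override it?** Protocol section 10 gives the SAP precedence where the two differ. The SAP states no interval for the AUC and no definition of Ctrough, so there is nothing to override 10.8.5.

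**The case against.** The best defence is that the protocol shows elsewhere what it means. Sections 1.4.2 and 1.6 and the PK text of 10.5.1 all treat trough as an end-of-interval value, the last of these by visit. A reader might infer from 10.8.5 that every reported Ctrough will be zero. The documents do not support that: they contradict each other and do not settle on zero.

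A reader might also infer that the AUC covers one day. Section 10.8.5 gives no unit, and its words point to the end of the dosing period, so this is a conflict between label and words. Hours is only a plausible reading, since the protocol's other AUCs use hours.

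No PK sample falls between 3-6 hours after the Day 1 infusion and Day 7, which may suggest that the sampling cannot support the AUC. That does not follow. Section 10.8.5 plans population PK and SAP 7.6 a compartmental model, and a model-derived AUC needs no sample at its endpoint.

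Nor is the interim objective of checking "predicted MAU868 plasma levels" defeated. The first review receives individual profiles. For the second, SAP 8.2.3 gives the review committee serum concentrations through Week 16, which takes in the pre-infusion samples on Days 28, 56 and 84 and the Day 112 sample. Finally, the documents give no half-life, so no firm fold can be put on the gap between the Day 252 value and the trough.

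These points limit the consequence. They do not remove the two faulty definitions, and the PK plan that might have replaced them is not available to read.

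**Conclusion.** The point holds as a conflict of definitions. The AUC label matches no interval in the design, and the Ctrough wording, taken literally over all samples, selects the drug-free Day 1 value in place of the predicted 172, 248 and 858 µg/mL. The damage is confined to the reported PK parameters and their comparability with the predicted trough and the monthly AUC. The primary safety objective and the interim review of concentrations are not affected.

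The predicted troughs and the 3.6% follow from the documents' figures; the 3.6% applies only if 24 means hours. The 2% to 5% share and the Day 252 range also rest on the assumed volume of 3 to 7 L and a one-compartment model. Whether the operative PK plan repeats the wording cannot be known from these documents. It should be corrected, but it does not threaten the trial.

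**What to change.** Amend Protocol 10.8.5 and carry the same text into the PK analysis plan.

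- **Ctrough:** the concentration at the end of each actual dosing interval, reported by dose. Nominally these are the pre-infusion samples on Days 28, 56 and 84, and Day 112 after the fourth dose. Exclude the Day 1 pre-dose sample and the Day 140 and Day 252 washout samples.
- **Off-schedule subjects:** use actual time since the last dose where dosing was off schedule, skipped or stopped. Protocol 5.3.1 allows an interim dose followed by a skipped one, and 3.3.2 re-times visits after early discontinuation, so nominal days are not always end-of-interval.
- **Missing samples:** do not let a missing sample enter Ctrough as zero.
- **AUC:** replace AUC0-24 with AUCtau over the 28-day interval, unit stated, for the first and last dose.
- **Matrix:** reconcile plasma in Protocol 10.8.5 with serum in the PK text of 10.5.1 and in SAP 6.1.4.

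The cost is wording. Every sample needed is already scheduled, and no analysis is added beyond the modelling already planned.

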10.8.6 Interim Analysis

Interim Analyses

Following completion of the 12-week treatment period of Cohort 1, unblinded safety and tolerability data (adverse events, clinical laboratories, vitals/physical exams and ECGs), efficacy data (BKV viral load in the plasma) and PK (MAU868 plasma levels) will be reviewed by the Sponsor Study Review Committee (SSRC). The treatment assignment in Cohort 1 will be unblinded; however, these data will not include associated subject or site identifiers. The objectives of this interim analysis are to evaluate whether four doses MAU868 1350 mg IV administered every 28 days for a total of 4 doses demonstrate:

- safety and tolerability signals compared to placebo
- a decrease in BK plasma viral load compared to placebo
- predicted MAU868 plasma levels

The conclusions from this first analysis will be used by the Sponsor to evaluate the safety and efficacy of MAU868 early-on in this first-in-patient study. Unless a significant safety issue related to administration of MAU868 has been identified, the conclusions will have no impact on Cohort 2 or the study's design.

Following completion of the 12-week treatment periods for Cohorts 1 and 2, cumulative unblinded data from both cohorts will be reviewed for safety and tolerability (adverse events, clinical laboratories, vitals/physical exams and ECGs), efficacy (BKV viral load in the plasma) and PK (MAU868 plasma levels). The treatment assignments will be unblinded; however, these data will not include associated subject or site identifiers. The objectives of this second interim analysis are to evaluate whether four doses MAU868 1350 mg IV administered every 28 days for a total of 4 doses or MAU868 6750 mg IV administered as a first dose followed by 3 more doses of MAU868 1350 mg IV administered every 28 days demonstrate:

- safety and tolerability signals compared to placebo
- a decrease in viral load compared to placebo
- predicted MAU868 plasma levels

Based on the SSRC's safety, efficacy and PK conclusions for Cohorts 1 and 2, the dosing regimen for Cohort 3 may be *adjusted* in dosage and/or duration; however, the dosage and duration for Cohort 3 will not exceed the dose already specified in the protocol. Cohort 3 will not be opened for screening and enrollment this evaluation has been completed

11 DATA MANAGEMENT AND RECORD KEEPING

11.1 Data Management

11.1.1 Data Handling

Data will be recorded at the site on eCRFs and reviewed by the CRA during monitoring visits. The CRAs will verify data recorded in the EDC system with source documents. All corrections or changes made to any study data must be appropriately tracked in an audit trail in the EDC system. An eCRF will be considered complete when all missing, incorrect, and/or inconsistent data has been accounted for.

11.1.2 Computer Systems

Data will be processed using a validated computer system conforming to regulatory requirements.

11.1.3 Data Entry

Data must be recorded using the EDC system as the study is in progress. All site personnel must log into the system using their secure username and password in order to enter, review, or correct study data. These procedures must comply with Title 21 of the Code of Federal Regulations (21 CFR Part 11) and other appropriate international regulations. All passwords will be strictly confidential.

11.1.4 Medical Information Coding

For medical information, the following thesauri will be used:

- Medical Dictionary for Regulatory Activities (latest) for medical history and adverse events
- World Health Organization Drug Dictionary for prior and concomitant medications

11.1.5 Data Validation

Validation checks programmed within the EDC system, as well as supplemental validation performed via review of the downloaded data, will be applied to the data in order to ensure accurate, consistent, and reliable data. Data identified as erroneous, or data that are missing, will be referred to the investigative site for resolution through data queries. The eCRFs must be reviewed and electronically signed by the Investigator.

11.2 Record Keeping

Records of subjects, source documents, monitoring visit logs, eCRFs, inventory of study drug, regulatory documents, and other Sponsor correspondence pertaining to the study must be kept in the appropriate study files at the site. Source data is defined as all information in original records and certified copies of original records of clinical findings, observations, or other activities in a clinical study necessary for the evaluation and reconstruction of the clinical study. Source data are contained in source documents (original records or certified copies). These records will be retained in a secure file for the period as set forth in the Clinical Study Agreement. Prior to transfer or

destruction of these records, the Sponsor must be notified in writing and be given the opportunity to further store such records.

12 INVESTIGATOR REQUIREMENTS AND QUALITY CONTROL

12.1 Ethical Conduct of the Study

Good Clinical Practice is an international ethical and scientific quality standard for designing, conducting, recording, and reporting studies that involve human subjects. Compliance with this standard provides public assurance that the rights, safety, and wellbeing of study subjects are protected, consistent with the principles that have their origin in the Declaration of Helsinki, and that the clinical study data are credible.

